Effect of Flumazenil on Hypoactive Delirium in the ICU: A Double-Blind, Placebo-Controlled Pilot Study

NCT: 02899156

Document Date: September 25, 2017

Document Type: Study Protocol with Statistical Analysis

Objectives

The primary objectives was to determine the effect of flumazenil on delirium-free days for critically ill patients with benzodiazepine-associated hypoactive delirium. Delirium free days were defined as the number of days in the first 14 days during which the patient was alive without delirium or coma from any cause

The primary safety objective was the occurrence of severe refractory agitation, which was defined as RASS of +2 to +4 that did not resolve by decreasing the infusion rate of study drug.

Secondary outcomes included probability of delirium resolution, ICU LOS, maximum rate and duration of study infusion, rescue sedative use, and mechanical ventilator-free days.

The hypothesis was that flumazenil continuous infusion may decrease duration of delirium by reversing benzodiazepine-associated hypoactive delirium.

Study Design

This was a single-center randomized, double-blind, placebo-controlled study. Critically ill adult patients with suspected BZD-associated hypoactive delirium may be eligible.

Upon completion of screening and determining eligibility, patients received a test dose of flumazenil. If response was noted (defined as a change in RASS of +1 to +2), patients were randomized to receive standard of care and placebo infusion or standard of care and flumazenil infusion.

Methods

The PI or a co-investigator screened for subjects for inclusion via a daily drug utilization report of benzodiazepine use in the Intensive Care Units. Upon pre-qualification via EMR screening, the investigator performed an in-person assessment to confirm inclusion criteria have been met and patients do not meet exclusion criteria.

Screening included:

- review of the subjects current and prior to admission medication list (via medication reconciliation performed by PI/pharmacy medication reconciliation team, or urine drug toxicity screen)
- review of past medical history (history of seizure, TBI, etc.) to identify exclusion criteria

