- to ensure proper safety monitoring, the PI, a member of the primary care, and the bedside nurse (administering) were present to monitor for any complications for 30 minutes after the last test dose.

Infusion titration post-randomization (ICU-only):

1. Responders to flumazenil:
 - standard of care + flumazenil 2.5 mg/50 mLs 0.9% NaCl, or 5% dextrose (0.05 mg/mL) IV continuous infusion
 - Dosing range: 0.025 mg/hr – 0.3 mg/hr (0.5 -6 ml/hr)
 - Start at @ 2 mLs per hour (0.1 mg/hr., 2.4 mg/24 hours)
 - Titration by 1 mL (0.05 mg) or as clinically indicated per study investigator every 60 minutes for target RASS (0 to +1)
**Patient care order placed for nurse to monitor RASS every 1 hour (standard of care is every 2 hrs.).
 - Maximum Rate: 6 mLs/hr. (0.3 mg/hr.)
 - If RASS +2 to +3, decrease dose by 0.05mg (1 mL) or as clinically indicated per study investigator every 60 minutes or HOLD if at the lowest rate of 0.025 mg/hr (0.5ml/hr) and re-assess in 1 hour.
 - If RASS +4, HOLD regardless of rate and re-assess in 1 hour.
 - standard of care + placebo (50 mLs 0.9% NaCl, 5% dextrose) IV continuous infusion

- Dosing range: 0.025 mg/hr – 0.3 mg/hr (0.5 -6 ml/hr)
 - Start at @ 2 mLs per hour
 - Titration by 1 mL (0.05 mg) or as clinically indicated per study investigator every 60 minutes for target RASS (0 to +1)
 - Maximum Rate: 6mLs/hr. (0.3 mg/hr.)
 - If RASS +2 to +3, decrease dose by 0.05mg (1 mL) or as clinically indicated per study investigator every 60 minutes or HOLD if at the lowest rate of 0.025 mg/hr (0.5ml/hr) and re-assess in 1 hour.
 - If RASS +4, HOLD regardless of rate and re-assess in 1 hour.
2. PI or co-investigator assessed patient response daily during the intervention phase (no longer than 72 hours).
- Daily interruption of infusion starting @ 0900 for 4 hours or until RASS of -1 to -2 .
 - A. Assess & document CAM-ICU and RASS BEFORE continuous infusion is interrupted
 - B. At the end of the interruption, assess patient’s RASS and CAM-ICU.
 - C. If patient regresses back to RASS -1 to -3 and CAM-ICU positive, then study infusion was restarted at the previous rate and re-assessed daily.
 - D. If daily interruption results in no change in RASS or CAM-ICU scores then study infusion was restarted @ the previous rate
 - Daily interruption occurred daily unless one of the following criteria were met resulting in discontinuation of study drug in the interim:
 - A. Primary attending caring for patient deemed discontinuation appropriate

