 - a. Primary care team must *prospectively* notify the PI if the primary care team wishes to interrupt or discontinue the study infusion to provide clinical care to the patient.
 - B. RASS +2 to +4 while on infusion and agitation not controlled with standard treatments (i.e. anti-psychotics)
 - C. Rescue benzodiazepine needed due to signs of withdrawal according to the SHOT Scale
 - D. Remains CAM-ICU negative after interruption
 - E. ICU discharge (determined by physical transfer to lower level of care)
 - F. Adverse event attributable to study drug (i.e. supraventricular arrhythmia, seizure)
3. If episodic sedation was needed for a procedure (i.e. bronchoscopy)
- Study drug could be held (i.e. 30-60 minutes prior) and once the procedure was completed the study infusion could be restarted at previous rate.

As delineated above, the primary investigator and co-investigators were active participants in the study from pre-screening, enrollment, data collection, and data analysis. Relevant staff, including nursing personnel and medical staff, were utilized for coordination purposes.

Statistical Analysis

Baseline characteristics included age, sex, ICU service, Sequential Organ Failure Assessment (SOFA) score, Charlson Comorbidity Index, days in hospital prior to enrollment, time since last benzodiazepine administration, benzodiazepine indication, lorazepam equivalents (lorazepam 1 mg = midazolam 2 mg = diazepam 5 mg), home benzodiazepine use, and RASS prior to test dose. The original sample size calculation indicated that 40 patients in each group were required to detect a 30% difference (sd \pm 2 d) in delirium-free days, assuming p value less than 0.05 and 80% power. Descriptive statistics and the Wilcoxon rank-sum test were performed. The Kaplan–Meier method was used to characterize the probability of being delirium and coma free.

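### The Kaplan–Meier curve for freedom from delirium and coma has no event, death or relapse rule, and would tend to overstate resolution if deaths are censored

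*Combined protocol and SAP*

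**What the plan says.** In the combined protocol and SAP, the Statistical Analysis section gives one sentence to this analysis: the Kaplan–Meier "method was used to characterize the probability of being delirium and coma free". The curve presumably serves an outcome listed under Objectives, "Secondary outcomes included probability of delirium resolution", but the document does not make that link. Neither place gives an event, a time origin, a horizon, a censoring rule, or a rule for death or relapse.

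Three other places come close, each for a different purpose:

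- Objectives, primary outcome: delirium-free days are "the number of days in the first 14 days during which the patient was alive without delirium or coma from any cause". This settles death for the day count only.
- Infusion titration post-randomization, daily interruption, item C: "If patient regresses back to RASS -1 to -3 and CAM-ICU positive, then study infusion was restarted". This foresees relapse, but as a rule for the infusion.
- Same section, criteria for discontinuing study drug, item D: "Remains CAM-ICU negative after interruption". This is the nearest text to sustained clearing, but it governs the drug and not the endpoint.

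**The concern.** Kaplan–Meier suits a single event that every patient still under observation could yet have. Two features of this setting do not fit.

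First, death. A patient who dies while delirious can never resolve. Censoring that patient gives the curve the survivors' later chance of resolution, so one minus the curve can exceed the proportion who actually resolve. If such deaths are unequal between arms, the comparison is distorted too.

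Second, relapse. Being free of delirium and coma is a state that patients can leave and re-enter. A first-event curve counts a patient as resolved for good from the first clearing.

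As the plan stands, two analysts could draw different curves from the same data, and either curve could disagree with the primary endpoint, which does not credit days after death or days back in delirium.

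**Working it through.** **Inputs.** From the documents: 40 patients per group (Statistical Analysis) and a 14-day window (Objectives, stated for the primary outcome and taken here as the curve's horizon). The documents give no resolution or mortality rate. Assumed: true resolution R = 60% by day 14, deaths without resolution D = 0, 5, 10 or 20%, and constant hazards.

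**The plan's own figure.** There is none for this curve. The one design figure, 40 per group, belongs to the day count and cannot be reproduced because the control mean is missing. With SD 2, 40 per group detects 2 × (1.960 + 0.842) × √(2/40) = 1.25 days, which at 30% implies a control mean of about 4.2 days. This has no bearing on the present point.

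**Step 1. Size of the excess if deaths are censored.** Let r and d be the hazards of resolution and of death without resolution. The proportion with neither by day 14 is S = 1 − R − D, and r/(r + d) = R/(R + D). With deaths censored, the curve estimates exp(−14r) = S^(R/(R+D)), so one minus Kaplan–Meier is 1 − S^(R/(R+D)).

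| Unresolved deaths | S | Exponent | One minus Kaplan–Meier | Excess over 60% |
|---|---|---|---|---|
| 0% | 0.40 | 1.000 | 60.0% | 0 |
| 5% (2 of 40) | 0.35 | 0.923 | 62.1% | 2.1 points |
| 10% (4 of 40) | 0.30 | 0.857 | 64.4% | 4.4 points |
| 20% (8 of 40) | 0.20 | 0.750 | 70.1% | 10.1 points |

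A daily-interval simulation of 400,000 patients gave 62.0, 64.1 and 69.6% at 5, 10 and 20% deaths with deaths censored. With deaths kept at risk as unresolved to day 14 it gave 60.1, 59.9 and 60.0%, equal to the simulated truth.

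**Step 2. Dependence on when deaths occur.** Take 40 patients, 2 resolving each day for 14 days, so true resolution is 28/40 = 70.0%. Let deaths fall one per day from day 1, each after that day's resolutions, and censor them.

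- 2 deaths: 1 − (38/40)(35/37)(10/34) = 73.6%.
- 4 deaths: 1 − (38/40)(35/37)(32/34)(29/31)(8/28) = 77.4%.
- 8 deaths, by the same steps: 86.3%.
- 8 deaths, all after the last resolution: 1 − 12/40 = 70.0%, no excess.

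So the excess needs a death that precedes a later resolution. Deaths alone are not enough.

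**Step 3. Comparison between arms.** With equal deaths the order of the arms is kept: a true 60% versus 50% appears as a gap of 10.4, 11.0 or 12.4 points at 5, 10 or 20% deaths.

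With unequal deaths, hold the resolution hazard at r = 0.0692 per day in both arms. Both curves then show 1 − exp(−14 × 0.0692) = 62.1%. True resolution is r/(r + d) × [1 − exp(−14(r + d))]:

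| Unresolved deaths | d per day | True resolution | Curve shows |
|---|---|---|---|
| 5% | 0.0058 | 60.0% | 62.1% |
| 10% | 0.0120 | 57.9% | 62.1% |
| 15% | 0.0186 | 55.8% | 62.1% |
| 20% | 0.0258 | 53.6% | 62.1% |

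Against a 5% arm, the curve hides a deficit of about 2, 4 or 6 points.

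**Step 4. Size relative to precision.** At 40 per arm the standard error is √(0.6 × 0.4/40) = 7.7 points for one arm and √(2 × 0.6 × 0.4/40) = 11.0 points for a difference.

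**Step 5. Relapse.** Each patient who has cleared and is delirious again on a given day lowers the proportion currently free by 1/40 = 2.5 points. A first-event curve does not move.

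**The case against.** The strongest reply is that nothing says deaths were censored. The phrase in Statistical Analysis resembles the primary endpoint, which requires the patient to be alive, so keeping deaths as unresolved is an available reading, and then there is no such bias. This stands. A reader might infer that the planned analysis is biased. The documents support only that the plan leaves the choice open and that the standard form of the named method is the unfavourable one.

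A reader might also infer that every unresolved death inflates the curve. Step 2 shows otherwise, and the constant-hazard figures are not a general result.

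A third tempting reading is that patients are censored on leaving the ICU, because "ICU discharge (determined by physical transfer to lower level of care") is a criterion for discontinuing study drug. The documents do not support it. Infusion lasts at most 72 hours while the primary outcome runs 14 days, so observation beyond the end of drug is already implied.

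The effect is also modest. At 5 to 10% deaths the illustrative excess is 2 to 4 points against a one-arm standard error of about 8, and the hidden deficits lie within the 11-point standard error of a difference. No test on the curve is named. All of this stands and sets the priority. It does not supply the missing rules, and a bias does not shrink with sample size as a standard error does.

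Finally, the only daily assessments described fall in the intervention phase, so the protocol does not show how status was recorded afterwards. That is fair, but the primary endpoint cannot be computed without it.

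**Conclusion.** The point holds as a conditional one. The plan names a method whose standard form does not fit an outcome with competing deaths and possible relapse, and it gives no rule that would correct this. If deaths are censored, resolution is overstated whenever an unresolved death precedes a later resolution, by 2, 4 or 10 points at 5, 10 or 20% deaths under the assumed 60% resolution and constant hazards. With the same number of deaths, the excess depends on their timing and falls to zero if all come after the last resolution. The true size, and the direction of any distortion between arms, cannot be known from the documents.

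Priority is low. The outcome is secondary, the curve is descriptive, the study is a pilot, and neither the primary endpoint nor the sample size is touched.

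**What to change.** Replace the Kaplan–Meier sentence with one or both of these, by arm:

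- The cumulative incidence of resolution to day 14 with death as a competing event (Aalen–Johansen). State the time origin and whether resolution means first or sustained clearing. Kaplan–Meier with deaths kept at risk as unresolved to day 14 gives the same answer only if there is no other censoring before day 14.
- The proportion alive and free of delirium and coma on each of days 1 to 14. This matches the primary endpoint and handles both death and relapse without an event definition.

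The cost is two or three sentences and slightly more analysis work, using the daily delirium, coma and vital status that the primary endpoint already requires. Because the document is largely written in the past tense, this may mean re-running an analysis already done. The resolution figures may come out less favourable.
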